3.2.3.10. Change in EQ-5D-5L scores from Baseline to the 12 month visit

- The EQ-5D is a utility scale consisting of three components: health state dimensions, health state thermometer scale and health state index.
 - The health state dimensions will be described by the 5 dimensions of the EQ-5D (mobility, self-care, usual activities, pain/discomfort and anxiety/depression). Each dimension has 5 response choices, listed in order of increasing severity.
 - The health state thermometer scale asks respondents to rate their present health status on a 0 to 100 visual analog scale (VAS). The change from Baseline visit to the 12 month visit in the VAS scores will be evaluated.
 - The health state index score will be calculated using the dimension scores from the 5 dimensions, ranging between 1.0 (best imaginable health) and -0.594 (worst imaginable health). The change from Baseline visit to the 12 month visit

in the health state index score will be evaluated.

3.2.3.11. Change in UPDRS Part II (ADL) from Baseline to the 12 month visit.

- The UPDRS part II (ADL) score will be calculated as the sum of the individual items 5-17. Missing individual items will not be imputed. If there is at least 1 missing item, the corresponding sum score will be set as missing.

3.2.3.12. Change in CGI-Severity (CGI-S) and CGI-Improvement (CGI-I) from Baseline to the 12 month visit

- The CGI-I scores will be categorized as improvements (very much improved, much improved, minimally improved) or non-improvements (no change, minimally worse, much worse, very much worse). For descriptive statistics, in case the CGI-I score is missing (or “Not assessed”) but the visit in question was done, the last non missing available data will be used for incomplete data.
- The changes from Baseline in CGI-S score will be categorized as improvements if the value at the visit in question is better than the baseline value. If the value at the visit in question is same or worse than the baseline value, the change is categorized as a non-improvement. “Normal, not at all ill” is considered as the best value and “Among the most extremely ill” the worst. For descriptive statistics, in case the post-baseline CGI-S score is recorded as “Not assessed”, but the visit in question was done, the last non missing available data will be used for incomplete data. In case the baseline value is missing or recorded as “Not assessed”, the change will be set as missing.

3.2.3.13. Change in SGI-Improvement from Baseline to the 12 month visit.

- This variable will be derived in a similar way as CGI-I described in 3.2.3.12.

3.2.3.14. Change in PDSS total score from Baseline to the 12 month visit.

- Each of the 15 items is scored on a 5-point scale (from 0 indicating no symptoms to 4 indicating maximum symptoms). The total score is calculated as a sum score of the 15 items. In case a single item is missing, the total score will be set as missing.

3.2.3.15. Change in UPDRS Part III (motor score) from Baseline to the 12 month visit.

- The UPDRS part III (motor) score will be calculated as the sum of the individual items 18-31. UPDRS scores will be gathered during visit but not at pre-specified time points. Missing individual items will not be imputed. If there is at least 1 missing item, the corresponding sum score will be set as missing.

3.2.3.16. Change in ND0612 Dose - Data on ND0612 dose reduction will be assessed as change from baseline in total daily of LD dose.

3.2.4. Additional Outcome Measures

- Data on malfunctions of the pump system will be evaluated as additional endpoints. The influence of the pump system malfunctions on the safety of ND0612 will be evaluated by capturing data on the date of malfunctions, including the description of the malfunction, association to an AE and action taken.

3.3. Determination of Sample Size

A sample size of 120-170 treated subjects is considered appropriate for evaluating the long-term safety and tolerability of ND0612 (administered as one of two regimens) with a focus on local safety at infusion sites. No formal sample size evaluation has been conducted. Since the maximum size of Cohort 1 is limited (36 subjects are to be treated in study ND0612H-006) the majority of subjects who completed the ND0612H-012 study will be included in Cohort 2.

3.4. Treatment Assignment & Blinding

This study investigates three dosing regimens of ND0612:

- Regimen 1 – ND0612 solution will be infused subcutaneously via 2 infusion sites for 24 hours continuously. Dosing will start at any time during the day which is convenient for the subject. The regimen will be comprised of two infusion rates: a fixed rate of 0.08mL/h for 6 hours (22:00-4:00-low night rate), which will then change automatically to a rate of up to 0.64 mL/h for 18 hours (4:00-22:00 high day rate). The dose will be delivered via two infusion sites in parallel, utilizing a pump system. The total infusion volume during a 24 hr period will be up to 12.00 ml (~6.00 ml from each infusion site) and deliver 720 mg LD and 90 mg CD.
- Regimen 2 – ND0612 solution will be infused subcutaneously via 2 infusion sites for 14 hours continuously. Dosing will start upon waking. The infusion will be set to a rate of 0.64 mL/h for 14 hours (high rate) from two infusion sites in parallel, utilizing a pump system. The total infusion volume during the infusion period will be up to 8.96 ml (4.48 ml from each infusion site) which is equivalent to delivery of 537.6 mg LD and 67.2 mg CD over the course of 14 hours. On 08 December 2016 the Sponsor made a decision to discontinue treatment Regimen 2

and switched all subjects who were receiving Regimen 2 to Regimen 1 at their next scheduled visit.

[figure not shown]
- Regimen 3 – ND0612 solution will be infused subcutaneously via 2 infusion sites for 16 hours continuously. Dosing will start upon waking. The infusion will be set to a rate of 0.75 mL/h for 16 hours from two infusion sites in parallel, utilizing the pump system. The total infusion volume during the infusion period will be up to 12 ml (6 ml from each infusion site) which is equivalent to 720 mg LD and 90 mg CD.

On 08 December 2016 (Amendment 1), the Sponsor decided to switch all subjects who were treated with Regimen 2 to Regimen 1. Following this decision, ongoing subjects treated with Regimen 2 were to be switched at their next scheduled study visit to Regimen 1. Ongoing subjects in cohort 1 who were treated with Regimen 2 were to be switched at their next scheduled study visit to Regimen 1. Subjects in cohort 2 who were not yet randomized were to be allocated to Regimen 1 instead of being randomized.

Following the approval of Protocol amendment 2 (dated 23 January 2017) all new subjects who were enrolled in Cohort 2 were assigned to treatment Regimen 3 (see dosing regimens for description of each regimen).

Unless stated otherwise, the subjects who received Regimen 2 and were switched to Regimen 1 during the study and will be included in the Regimen 1 group.

Figure 1: Cohorts and Regimen Changes following Protocol Amendments

3.5. Sequence of Planned Analyses

3.5.1. Interim Analyses

No interim analysis is planned for this study.

3.5.2. Final Analyses and Reporting

All final, planned analyses identified in this SAP will be performed only after the last patient has completed 12 months. Database lock will not be performed until this SAP has been signed and approved. Any exploratory analyses completed to support study analyses, which were not identified in this SAP, will be documented and reported in appendices to the CSR.

The safety data from the optional treatment extension will be combined with the safety data of the main study and will be analyzed similarly as defined below using the Follow-up Safety Set. These analyses will be defined in more detail in a separate SAP for the optional treatment extension period.

4. ANALYSIS SETS

The following analysis sets will be defined:

4.1. All screened subjects

This Analysis set consists of all patients who underwent screening and will be used for summary of disposition and data listings.

4.2. Intention-to-Treat (ITT):

The ITT set will include all subjects who were randomized (before Amendment 1) or enrolled (after Amendment 1) to the study. The subjects will be grouped according to the randomized (before Amendment 1) or allocated (after Amendment 1) treatment regimen.

4.3. Safety Set:

The Safety Set will consist of all subjects (cohort 1 and cohort 2) receiving at least 1 dose of study drug (ND0612). The subjects will be grouped according to the treatment regimen actually received. The Safety Set will be used for all summaries of safety and tolerability data.

4.4. Modified Intention-to-Treat (mITT) Set:

The mITT is a subset of the ITT analysis set. The mITT Set for cohort 2 will include subjects having ON/OFF Home diary data at baseline and at least one valid post-baseline measurement. The mITT Set for in cohort 1 will include subjects having UPDRS (part III) efficacy data at baseline and at least one valid post-baseline UPDRS (part III) measurement. The subjects will be grouped according to the randomized (before Amendment 1) or allocated (after Amendment 1) treatment regimen. The mITT Set will be used for all summaries and analyses of efficacy data.

Unless stated otherwise, the subjects who received Regimen 2 and were switched to Regimen 1 during the study will be included in the Regimen 1 group. However, sensitivity analyses will be conducted by excluding the subjects who were randomized to receive Regimen 2, as specified later in this SAP.

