11.1.1 Datasets or Populations Analyzed

The All Enrolled Set will consist of all enrolled subjects. All listings will be produced for the All Enrolled Set.

The Safety Set will consist of all subjects receiving at least 1 dose of study drug (ND0612). The Safety Set will be used for all summaries of safety and tolerability data. In addition, summaries of baseline and demographic data will also be produced for the Safety Set.

The modified Intention-to-Treat (mITT) Set will include all enrolled subjects who have valid efficacy data at baseline and at least once after the baseline. The efficacy analysis will be based on the mITT Set. The mITT Set will be used for all summaries and analyses of efficacy data.

The earlier version of this protocol included a randomization of subjects to Regimen 1 or Regimen 2. Unless stated otherwise, the subjects who received Regimen 2 and were switched to Regimen 1 during the study conduct will be included in the Regimen 1 group.

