1. PREFACE

This Statistical Analysis Plan (SAP) describes the planned analysis and reporting for NeuroDerm clinical trial ND0612H-012 (A multicenter, international, open-label, safety study of ND0612, a solution of levodopa/carbidopa delivered via a pump system as a continuous subcutaneous infusion in subjects with advanced Parkinson's Disease (BeyoND)), and was written in accordance with SOP 002 - Statistical Analysis Plan (NStat – [REDACTED] Procedure). The structure and content of this SAP provides sufficient details to meet the requirements identified by the FDA and International Conference on Harmonization of Technical Requirements for Registration of Pharmaceuticals for Human Use (ICH): E9 Guidance on Statistical Principles in Clinical Trials. All work planned and reported for this SAP will follow internationally accepted guidelines, published by the American Statistical Association, and the Royal Statistical Society, for statistical practice.

The following documents were reviewed in preparation of this SAP:

- Clinical Study Protocol ND0612H-012 Version 9.0 (global Amendment 8): issued on, July 11th 2019
- Case report form (CRF) for ND0612H-012
- ICH E9 Guidance on Statistical Principles for Clinical Trials.
- ICH E3 Structure and Content of Clinical Study Reports (CSRs)

This SAP describes the statistical analyses as it is foreseen before final database lock. The SAP will serve as a complement to the study protocol and supersedes it in case of differences between the SAP and the statistical sections of the protocol. In case of major differences, e.g. changes in the analysis related to the primary endpoint, a protocol amendment will be considered. The SAP may be updated during the study conduct and will be finalized before final database lock.

Based on FDA correspondences dated 27th of March 2019, Neuroderm was advised to focus its safety analysis on AE of Special Interest (AESI), specifically for Infusion Site Skin Reactions (ISR's). In addition, all cases of hypersensitivity reactions (e.g., diffuse skin rash, anaphylaxis and angioedema) should be considered AESI. Cases of Polyneuropathy were also considered as AESI.

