8. EFFICACY

8.1. General

For the efficacy endpoints, continuous data will be summarized at each protocol scheduled visit, by treatment regimen, using summary statistics. Actual values and changes from baseline will be presented. All categorical endpoints will be summarized at each protocol scheduled visit, by treatment regimen, using frequency tabulations.

As the primary and secondary purpose of this study is to explore the 2 treatment regimens with regards to safety and efficacy and not to perform confirmatory analyses comparing the treatment regimens, there will be no formal hypothesis testing performed and adjustments for multiplicity are not required.

The analyses of the efficacy data will focus on estimating the changes from baseline of the present study for cohort 2 and from baseline of 006 study for cohort 1. Cohort 1 and Cohort 2 will be analyzed separately and combined. Data from Cohort 2 will be summarized by treatment group (Regimen 1 or Regimen 3), i.e. the summaries of efficacy data will include the following groups: Cohort 1/Regimen 1, Cohort 2/Regimen 1 and Cohort 2/Regimen 3. For the combined cohort analysis Regimen 1 and Regimen 3. The mITT set will be used for all efficacy analyses.

Sensitivity analyses of efficacy data will be conducted by excluding the patients who were randomized to receive Regimen 2. These analyses will be done for the “ON” time without troublesome dyskinesia.

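### The Cohort 2 mITT set is tied to the ON/OFF diary but used for every efficacy endpoint, so subjects with usable scale data and no qualifying diary drop out of those analyses

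*SAP*

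**What the plan says.** For Cohort 2, SAP 4.4 reads: "The mITT Set for cohort 2 will include subjects having ON/OFF Home diary data at baseline", and adds that one or more valid measurements after baseline are needed, without naming the instrument. For Cohort 1 the same section uses UPDRS Part III instead, at baseline and with "at least one valid post-baseline UPDRS (part III) measurement". Each cohort's set thus rests on one instrument.

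The scope is unrestricted. SAP 4.4 says: "The mITT Set will be used for all summaries and analyses of efficacy data". SAP 8.1 repeats it: "The mITT set will be used for all efficacy analyses". No endpoint has its own evaluable set. The ITT set of SAP 4.2 serves disposition and baseline tables, not efficacy. The only population sensitivity analysis (SAP 8.1) removes subjects randomized to Regimen 2, and only for ON time without troublesome dyskinesia.

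Protocol 11.1.1 (version 10.0) is broader. Its mITT set takes "all enrolled subjects who have valid efficacy data at baseline and at least once after the baseline", with no instrument named. The SAP's preface settles which text governs: the SAP "supersedes it in case of differences between the SAP and the statistical sections of the protocol". SAP section 10 declares no changes from protocol version 9.0, which is not among the documents.

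**The concern.** Eight of the efficacy measures in SAP 8.2.6 to 8.2.12 need no diary: PDQ-39, EQ-5D-5L, UPDRS Part II, UPDRS Part III, CGI-S, CGI-I, SGI-I and PDSS. They are collected at clinic visits, independently of a form the subject fills in at home. Making a diary the condition for analysing them removes data already collected, for a reason unrelated to the endpoint.

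Three things are at stake:

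- precision on the scale endpoints;
- possible selection, because those who return usable diaries may differ from those who do not;
- coherence of the combined-cohort analyses in SAP 8.1, where subjects would enter under different rules depending on their cohort.

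**Working it through.** The plan gives no figure for this point, so there is none to reproduce. The check sets the rule against the schedule and the missing-data section, then sizes it under a stated assumption.

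**1. Who is excluded.** A Cohort 2 subject with no baseline diary is out of every efficacy analysis on any reading of SAP 4.4. A subject with a baseline diary but no valid later diary is out if the post-baseline measurement means a diary.

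**2. How a diary can be missing when scales are present.**

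- SAP 3.2.3.1 needs 44 of 48 half-hours completed for a valid day, that is 44 / 2 = 22 hours. Protocol 10.2.1.1 asks for entries in waking hours. A 16-hour waking day gives 16 × 2 = 32 entries, so the day fails unless sleep is also marked.
- Protocol 10.2.1.2 to 10.2.1.5 schedule UPDRS, CGI, SGI-I, PDSS and PDQ-39 at Week 1 and at early termination. The protocol's first post-baseline diary is at Month 1, and an early-termination diary is collected only where feasible. SAP 3.2.3.1 does list a Week 1 diary, so the two documents disagree here.

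**3. Conflict with SAP 5.4.** That section (like protocol 11.1.7) keeps prematurely withdrawn subjects in all analyses whatever their time on treatment, and assigns early-termination data to the closest visit when that visit is missing. Take a subject who leaves at about Day 21. That is 21 − 7 = 14 days from Week 1 and about 30 − 21 = 9 days from Month 1, so an early-termination UPDRS or PDSS score becomes the Month 1 value, and Month 1 is in the MMRM of SAP 8.2.1. Without a qualifying diary the subject is nevertheless outside the mITT set. For categorical endpoints, SAP 5.4 carries the last value forward, so a Week 1 CGI-I or SGI-I rating could also have counted later.

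**4. Combined cohorts.** The combined analysis in SAP 8.1 is by Regimen 1 and Regimen 3. Combined Regimen 1 would pool Cohort 1 subjects selected on UPDRS Part III with Cohort 2 subjects selected on the diary. Regimen 3 is Cohort 2 only, hence wholly diary-selected. A regimen comparison on, say, PDSS would rest on unlike inclusion rules.

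**5. Size.** Let f be the share of Cohort 2 without a qualifying diary. It is not in the documents; 5% to 15% is an assumption. Cohort 1 is at most 36 (protocol 11.2, SAP 3.3).

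- Subjects affected = f × N.
- Inflation of the standard error = 1/√(1 − f) − 1.

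| Source of total | Cohort 2 N | f = 5% | f = 15% |
|---|---|---|---|
| Protocol 11.2, about 210 | 210 − 36 = 174 | 8.7 | 26.1 |
| SAP 3.3, lower end 120 | 120 − 36 = 84 | 4.2 | 12.6 |
| SAP 3.3, upper end 170 | 170 − 36 = 134 | 6.7 | 20.1 |

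Standard-error inflation is 1/√0.95 − 1 = 2.6% at f = 5% and 1/√0.85 − 1 = 8.5% at f = 15%. Both the counts and the inflation are upper values for a given f and N, because they assume that every excluded subject has usable scale data.

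**The case against.** One efficacy population per cohort, anchored on the first-listed efficacy endpoint, is a defensible convention and keeps the same subjects across tables. Efficacy is exploratory (protocol 7.3, SAP 8.1), and the primary safety and tolerability analyses use the Safety Set. This stands, and it limits the importance of the point. It does not explain why a diary should decide who is analysed for UPDRS.

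Diary failure may also be uncommon. One valid day is enough, the days may fall within 7 days of the visit (SAP 3.2.3.1), and the protocol provides diary training, reminder calls and site review of entries. A subject must lack a valid day at every post-baseline diary visit to fail on that side. This too stands, and is a reason to treat 5% to 15% as illustrative.

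Several stronger readings are tempting but not supported:

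- *That SAP 4.4 expressly demands a valid diary at both times.* The baseline clause does not say valid, and the post-baseline clause does not name the diary, whereas the Cohort 1 sentence names UPDRS Part III. The baseline diary condition is explicit; the later one is only the natural reading.
- *That anyone leaving after Week 1 loses modelled data.* The MMRM visits are Months 1 to 12. A subject with Week 1 data alone would not enter those models under any set; the loss there is Week 1 summaries and carried-forward categorical ratings. EQ-5D-5L is not collected at Week 1 at all.
- *That the rule favours responders.* Nothing in the documents shows a direction, and an endpoint-specific set also requires a post-baseline value.
- *That the SAP departed from its own protocol without saying so.* It was written to version 9.0, which is not available; the difference is shown only against version 10.0.

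**Conclusion.** The point holds in limited form. As written, SAP 4.4 and 8.1 leave Cohort 2 subjects without a qualifying diary out of eight measures that need no diary, with no ITT efficacy analysis to bring them back and in conflict with SAP 5.4. The data remain in the listings (SAP 5.1), so they are left unanalysed rather than lost.

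Assuming 5% to 15% without a qualifying diary, about 9 to 26 of about 174 Cohort 2 subjects are affected on the protocol's total, or about 4 to 20 of 84 to 134 on the SAP's. The consequence is a modest loss of precision and possible selection of unknown direction. The core conclusion rests only on the explicit baseline diary condition; the numbers rest on the assumed share and on Cohort 1 reaching 36. No safety or tolerability result is affected.

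**What to change.** - In SAP 4.4, define evaluability by endpoint: enrolled subjects with a valid baseline value and at least one valid post-baseline value of the endpoint being analysed. Apply the same rule to both cohorts, so that combined analyses share one rule.
- Keep the diary condition for the diary endpoints only, and state that both the baseline and the post-baseline values must be valid diaries.
- Amend the scope sentences in SAP 4.4 and 8.1 to match.
- Reconcile the Week 1 diary in SAP 3.2.3.1 with the protocol schedule and with the MMRM visits in SAP 8.2.1.
- Record the change in SAP section 10.

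This is a cheap improvement: wording and programming only, with no new data or visits. The cost is that N will differ between endpoints, so each table should state its own N.

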4.5. Sub-group Analysis Sets

The following subgroups may be explored, e.g. for the “ON” time without troublesome dyskinesia:

ND0612H-012

Final 4.0

- Patients with the baseline “ON” time without troublesome dyskinesia less than or equal to the median versus patients with baseline “ON” time without troublesome dyskinesia above the median
- Patients with low total daily levodopa dose at baseline (<400 mg) versus patients with high total daily levodopa dose at baseline (\geq 400 mg)
- Non-elderly (<65 years) versus elderly (\geq 65 years) patients
- Male versus female patients
- Patients with 1 hour or more of troublesome dyskinesia at baseline vs. Patients with less than 1 hour.
- Patients enrolled in USA versus EU+Israel (Eastern+Western+Israel)

In case any subgroup analysis will be performed, the corresponding demographic and baseline data will be summarized.

5. GENERAL ASPECTS FOR DATA ANALYSIS

5.1. General Methods

All data from all patients entered into the study will be included in patient data listings. The listings will be sorted by center, and patient number (and by visit, if applicable).

The data will be summarized using either descriptive statistics (number of non-missing observations, mean, median, SD, standard error of the mean (SEM), minimum and maximum) for continuous data or frequency counts and percentages for categorical data. For visit-specific data, the number of subjects with non-missing observations at the visit in question will be used as the denominator for percent calculations. Unknown, Not Done, Not Applicable and other classifications of missing data will not be considered.

The summaries will be broken down by treatment regimen (Regimen 1, Regimen 3) and by visit, as applicable. For demographic and other baseline characteristics and selected safety data, an overall column will be displayed in addition to the data broken down by the treatment regimen. Unscheduled or repeated assessments will not be included in summary tables but will be included in listings.

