10.1.6 Neurological Examination

A neurological examination will be performed by an investigator who is a neurologist by medical training at Screening, Day 1, the 1-month safety follow-up visit, and the Early termination visit (if applicable). Any changes during the treatment period will be recorded on the eCRF.

10.1.7 12-lead ECG

A resting 12-lead ECG will be performed at Screening and the clinic visits on Week 1, Months 1, 2, 3, 4, 6, 9, 12, Safety FU visit 1, and Early Termination visit (if applicable). In the event of possible ECG findings, additional ECG reads can be added at follow-up visits. The ECG evaluation will be performed centrally by Biomedical Systems (see Section 2) with the following exception: ECG data obtained at the safety follow-up visits after the extension periods (see Section 9.2.4) and at early termination visits during the extension periods (see Section 9.2.8) will be analysed locally. ECG abnormalities will be recorded on the eCRF.

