5.5. Study Days and Visit Windows

Study days will be numbered relative to the first day of study drug administration. The start of treatment (day 1) is defined as the date on which a patient takes the first dose of study drug, as recorded in CRF. Days will be numbered relative to study start (ie, ..., -2, -1, 1, 2, ...; with day 1 being the start of study drug and day -1 being the day before the start of study drug).

The study data will be summarized as collected at the scheduled study visits regardless of visit window violations. For by-visit summaries, if there are multiple assessments at a post-baseline visit, then the last non-missing assessment at that visit will be used for the summary.

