7.5.1. Clinical Laboratory Evaluations

All laboratory data (hematology and biochemistry), including dipstick urinalysis results will be summarized with descriptive statistics (continuous variables) or as distributions (categorical variables) by visit and treatment group. In addition, the changes from baseline will be summarized as well as the number and percentage of patients with normal or abnormal (i.e., out of reference range) values at each visit for each parameter by treatment group. The out-of-range values will be further classified as clinically significant and clinically not significant based on the investigator's interpretation.

Furthermore, values of selected laboratory parameters will be classified as potentially clinically significant using the following criteria and tabulated in addition to the criteria for abnormality and clinical significance defined above:

- Albumin-L (< 2.5 g/dl)
- Alkaline Phosphatase-H (> 400 U/L)
- Bilirubin, total-H (> 2 mg/dl)
- BUN-H (> 30 mg/dl)
- Calcium-L (< 7 mg/dl)
- Calcium-H (> 12 mg/dl)
- Cholesterol-H (> 300 mg/dl)
- Creatinine-H (> 2 mg/dl)
- GGT-H (> 3XULN)
- Glucose-L (< 50 mg/dl)
- Glucose-H (> 250 mg/dl)
- Phosphorus-L (< 2.0 mg/dl)
- Phosphorus-H (> 5.0 mg/dl)
- Potassium-L (< 3.0 mmol/L)
- Potassium-H (> 5.5 mmol/L)
- SGOT/AST-H (> 3XULN)
- SGPT/ALT-H (> 3XULN)
- Sodium-L (< 130 mmol/L)
- Sodium-H (> 150 mmol/L)

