7.5.2. Vital Signs

Vital sign measurements include heart rate (HR), supine and standing blood pressure (BP) (both systolic and diastolic), body temperature, and weight. Furthermore, supine minus standing blood pressure (both systolic and diastolic) will be calculated. The data will be summarized with descriptive statistics by visit and treatment group. In addition, the changes from baseline will be summarized with descriptive statistics.

Furthermore, to identify potentially clinically significant vital signs, the following criteria will be used and tabulated as a shift table by visit:

- Systolic Blood Pressure: <90 mmHg (low), 90-140 mm Hg (normal), >140 mmHg (high)
- Diastolic Blood Pressure: <90 mmHg (low), 90-100 mmHg (normal), >100 mmHg (high)
- Heart Rate: <60 beats per minute (low), 60-100 beats per minute (normal), >100 beats per minute (high).

Orthostatic hypotension will be defined as a reduction in systolic BP of 20 mmHg or more, and/or a reduction in diastolic BP of 10 mmHg or more, for the standing measurement compared to the supine measurement. The proportion of patients with orthostatic hypotension will be tabulated as a shift table by visit and treatment group.

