7.5.3. ECG

The ECGs will be assessed by the investigator and deemed “Normal”, “Abnormal, not clinically significant” and “Abnormal, clinically significant” and tabulated by visit and treatment group.

In addition, the numerical ECG data generated by the central ECG laboratory will be summarized by descriptive statistics for each parameter by visit and treatment group. Also the changes from baseline will be summarized.

The QTc intervals fulfilling the following criteria will be tabulated separately using Fridericia’s correction:

- Values >500 msec
- Values increasing >15% from baseline if baseline value is ≥ 440 msec
- Values increasing >30% from baseline if baseline value is <440 msec

- Values increasing >30 msec from baseline
- Values increasing >60 msec from baseline.

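### SAP 5.1 keeps unscheduled and repeat readings out of every summary table, including the laboratory, blood-pressure and QTcF threshold tables, so these can undercount subjects who ever crossed a limit

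*SAP*

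**What the plan says.** SAP 5.1 (General Methods) sets a rule for all tables: "Unscheduled or repeated assessments will not be included in summary tables but will be included in listings".

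SAP 5.5 (Study Days and Visit Windows) has a second rule, limited to by-visit summaries: "if there are multiple assessments at a post-baseline visit, then the last non-missing assessment at that visit will be used for the summary".

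The tables at issue are secondary safety tables:

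- **Laboratory, SAP 7.5.1:** "values of selected laboratory parameters will be classified as potentially clinically significant using the following criteria and tabulated".
- **Vital signs, SAP 7.5.2:** "the following criteria will be used and tabulated as a shift table by visit". For orthostatic hypotension: "The proportion of patients with orthostatic hypotension will be tabulated as a shift table by visit and treatment group".
- **QTc with Fridericia's correction, SAP 7.5.3:** "The QTc intervals fulfilling the following criteria will be tabulated separately". The criteria include values above 500 msec and rises of more than 30 and 60 msec.

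None of these sections says which readings count, mentions unscheduled or repeat values, or asks for a worst post-baseline value. The protocol does not fill the gap. Its sections 11.1.3.2 and 11.1.4.2 leave the detail of these analyses to the SAP, and the SAP Preface gives the SAP precedence over the protocol's statistical sections.

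**The concern.** Leaving unscheduled readings out is sensible for by-visit means, where they would distort the time course. A threshold table has a different purpose: it counts who crossed a limit, whether or not the investigator called it an event.

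The readings left out are not a random sample. For ECGs, Protocol 10.1.7 says: "In the event of possible ECG findings, additional ECG reads can be added at follow-up visits". Protocol 9.2.9 names tolerability problems and down-titration as reasons for an unscheduled visit, and note g to the schedule in 8.1.2 allows safety assessments there. Protocol 10.1.2 expects repeat and unscheduled blood samples. Protocol 8.4.9.3 requires a clinic visit for every pump-rate change and gives persisting dopaminergic complications as a reason to reduce the rate. Protocol 11.1.3.2 singles out orthostatic blood pressure as a possible dopaminergic effect.

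Late in the main study, scheduled visits are three months apart (Months 6, 9 and 12). An unscheduled reading may then be the only record of a transient exceedance. At stake is whether these tables, in a study whose primary objective is long-term safety, report how many subjects ever crossed a limit.

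**Working it through.** The plan states no figure on this point, so there is none to reproduce. The check is to apply the rules to each pattern of readings.

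**1. Which rule reaches which table.** SAP 5.1 covers every summary table, so it reaches all four. SAP 5.5 covers by-visit summaries. The vital-sign and orthostatic tables are expressly by visit. The laboratory and QTc threshold tables are not stated to be, so 5.5 reaches them only if they are built that way.

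**2. What happens to each pattern.**

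| Where the exceedance is seen | Under 5.1 alone | If 5.5 governs same-visit repeats |
|---|---|---|
| Unscheduled assessment only | Not counted | Not counted (5.1 still removes it) |
| First scheduled reading; normal recheck at the same visit | Counted | Not counted |
| Same-visit repeat only, last at its visit | Not counted | Counted |

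The first row is certain. The other two depend on which rule prevails, and the SAP does not say.

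**3. Example with assumed QTcF values (msec).** Month 1 first reading 505, Month 1 repeat 470, unscheduled reading 512, Month 3 reading 455; criterion above 500.

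- All readings: maximum 512, counted.
- 5.1 alone, with 470 and 512 removed: maximum of 505 and 455 is 505, counted.
- 5.5 for the Month 1 pair, with 512 removed by 5.1: maximum of 470 and 455 is 470, not counted.
- If the Month 1 first reading had been normal, the 512 would be missed under either rule.

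**4. Direction.** For the number of subjects who ever exceed a limit, removing readings leaves the count unchanged or lowers it. This does not hold for counts at a single visit, where 5.5 can move a subject either way.

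**5. Illustration of size, on assumed inputs only.** Let p be the share of subjects with any exceedance (2% to 10% assumed) and s the share of those whose only exceedance is on a reading left out of the table (10% to 30% assumed). N is about 210 (Protocol 11.2) or, at the low end, 120 (SAP 3.3). The expected number with any exceedance is N × p and the expected number tabulated is N × p × (1 − s). The chance that at least one subject is missed is 1 − (1 − p × s)^N.

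| N | p | s | With any exceedance | Tabulated | Chance of missing at least one |
|---|---|---|---|---|---|
| 210 | 2% | 10% | 4.2 | 3.78 | 34% |
| 210 | 10% | 30% | 21.0 | 14.7 | 99.8% |
| 120 | 2% | 10% | 2.4 | 2.16 | 21% |
| 120 | 10% | 30% | 12.0 | 8.4 | 97% |

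The spread shows how far the answer depends on p and s. It says nothing about this trial's actual rates.

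**The case against.** **The values are not lost.** SAP 5.1 keeps them in listings. Protocol 10.1.1 lets an abnormal laboratory finding be an adverse event, Protocol 9.2.9 has AEs recorded at every unscheduled visit, and Protocol 10.1.7 has ECG abnormalities entered in the eCRF. An exceedance reported as a treatment-emergent AE reaches the TEAE tables. This stands and limits the harm. It does not remove the point, because AE reporting depends on the investigator's judgement and a listing gives neither count nor denominator.

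**The exposure may be small.** Protocol 9.2.3 schedules a single ECG per visit, and extra reads are placed at follow-up visits, so same-visit ECG repeats are not the planned pattern. The required content of an unscheduled visit is medication, AEs, date, reason and infusion-site assessment; laboratory tests, ECG and vital signs are discretionary. This also stands, and it is one reason why the effect cannot be sized.

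**Rechecks do not generally overwrite abnormal values.** A reader might infer that a QTcF above 500 msec, repeated at a lower value, always drops out. The documents do not support that. Under 5.1 the repeat is dropped and the first reading counts. The overwrite needs 5.5 to prevail over 5.1 and, for laboratory and QTc tables, a by-visit layout that is not stated.

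**Early-termination values.** A reader might infer from SAP 5.4 that these are excluded too. That rule is written for efficacy data, and no rule is found that removes early-termination safety values.

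**Conclusion.** The point holds in a limited form. As written, the SAP leaves out of its laboratory, vital-sign, orthostatic and QTcF threshold tables any exceedance seen only at an unscheduled assessment. It also leaves the handling of same-visit repeats undecided between 5.1 and 5.5. Counts of subjects ever exceeding a limit can only be unchanged or too low. By how much cannot be determined from the documents, which give neither exceedance rates nor the frequency of extra readings.

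The conclusion rests on reading 5.1 as applying to every table, which its place under General Methods and the silence of 7.5.1 to 7.5.3 support. A reader might go further and infer that the study's main safety result is biased. It is not: the primary analysis uses AEs with a focus on AESIs, VAS pain and tolerability, and none of these is built from the threshold tables. This is a cheap improvement to secondary tables, not a flaw in the primary analysis.

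**What to change.** Make three changes to the SAP:

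1. In 5.1, keep the scheduled-visit rule for by-visit descriptive statistics and state that it does not apply to the any-post-baseline rows below.
2. Reconcile 5.1 and 5.5 so that one rule says which reading is used when an assessment is repeated at the same visit.
3. In 7.5.1, 7.5.2 and 7.5.3, add to the laboratory, vital-sign, orthostatic and QTcF threshold tables an any-post-baseline row per subject. It uses the worst value from all post-baseline assessments, including unscheduled and repeat ones. The denominator is Safety Set subjects with at least one post-baseline value of that parameter.

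The cost is a few sentences and one derived worst-value record per parameter (one for each direction where the SAP lists both a low and a high limit). No new data are needed and no planned table is removed. The downside is that outlier counts may look slightly less favourable.
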